11.4.1.2 SERIOUS ADVERSE EVENTS

Any SAE experienced by the subject from signing the ICF through to 40 days after the last dose of study drug, regardless of severity or causality, must be recorded on the eCRF and SAE forms. Subjects visit the clinic 40 days after their last dose to gather information on ongoing AEs and report any new SAEs since the last study visit.

The study site must formally notify the Sponsor (or delegate) of the SAE within 24 hours from the time the study site becomes aware of the SAE. A formal notification must be submitted to the Sponsor regardless of the following:

- Severity
- Causality
- Whether or not the subject received study treatment or underwent study related procedures

The IRB/IEC will be notified as required by local regulations. The investigator will be responsible for submitting the required safety information to the appropriate IRB/IEC, including any safety reports received from the Sponsor as well as any SAEs occurring at his/her site.

The Sponsor, or designee, will prepare any required safety reports for Competent Regulatory Authorities and all active investigators. These reports will be provided as addenda to the IB, and the investigator will place these with the IB. All Competent Regulatory Authorities will be informed as per applicable legislation.

11.4.1.3 DEATH

Any event with an outcome of death should be appropriately recorded in the eCRF. All identified causes of death, including an assessment of the possible relationship of each to study treatment, must be reported as SAEs as outlined in Section 11.4.1.2. Any autopsy or other postmortem findings (including a coroner's report) should be provided if available.

11.4.1.4 ABNORMAL LABORATORY VALUES

All central laboratory data generated during the study will be included in standard Statistical Analysis System (SAS) datasets. Throughout this study, subjects will have samples sent to local laboratories and to the central laboratory. Only the values from the central laboratory will be captured in the database and used for the safety analysis.

Investigators may report AEs based upon local laboratory values, if clinically relevant. In this event, the actual value and the normal range for the local laboratory should be recorded on the AE eCRF.

11.4.2 SAFETY MONITORING

All AEs should be monitored by the investigator until resolution or stabilization.

11.4.2.1 SAFETY MONITORING COMMITTEE

The safety of study subjects will be monitored throughout the study on an ongoing basis. Given the double blind, placebo-controlled design of Study RA101495-02.202, this standard safety data review will be performed while blinded to treatment assignment.

If an additional data review should become necessary to ensure subject safety, a separate supervisory committee (i.e., an SMC) will convene and evaluate study data as appropriate. To ensure the scientific integrity of the study, members of the SMC will not be directly involved in management of the study.

11.4.2.2 POST-STUDY EVENTS

Any SAE that was continuing at the time of subject discontinuation or study completion should be monitored by the investigator until resolution or stabilization.

SAEs that occur within 40 days after the subject discontinues from or completes the study should be reported using the same procedures outlined in Section 11.4.1.2. These SAEs should be recorded in the eCRF. Subjects will visit the clinic 40 days after their last dose of study drug to gather information on ongoing AEs and report any new SAEs since the last study visit (see Section 11.4.1.2 for SAE reporting instructions). All SAEs will be followed to resolution or stabilization.

11.4.2.3 EMERGENCY UNBLINDING

The study drug treatment assignment may be unblinded only in emergency situations when knowledge of the treatment assignment is considered absolutely necessary for medical management of the subject or for clinical decision-making (i.e., when knowledge of the treatment assignment would impact a treatment decision). The investigator will have unrestricted and immediate access to unblind the treatment code in the interactive voice/web response system (IXRS). The instructions for unblinding a subject in the IXRS can be found in the IXRS User Guide.

In the event unblinding is necessary, the investigator is strongly encouraged, but not required, to contact the appropriate medical monitor to discuss the situation and the subject's medical status prior to unblinding.

When a subject's treatment assignment is unblinded, a comprehensive source note must be completed by the unblinding investigator that includes the date and time and the reason(s) the subject's treatment code was unblinded. In the event the investigator chooses to discuss the unblinding with the medical monitor, the source note must also include a record of the discussion.

It is mandatory that all personnel who are involved in the unblinding and who have access to the unblinded treatment assignment information maintain the confidentiality of the information by not divulging the treatment assignment.

Following emergency unblinding, the subject's further participation in the study should be discussed with the medical monitor.

11.5 SPECIAL CIRCUMSTANCES

11.5.1 PREGNANCY

Subjects and their partners should avoid pregnancy throughout the course of the study. Pregnancy in a study subject or partner must be reported to the Sponsor within 24 hours of the study site becoming aware of the pregnancy. Subjects with a positive pregnancy test before study drug dosing must not be dosed.

Information regarding a pregnancy occurrence in a study subject or partner and the outcome of the pregnancy will be collected.

Pregnancy in a study subject or partner is not, in itself, considered an AE. However, the medical outcome of an elective or spontaneous abortion, stillbirth, or congenital anomaly is considered an SAE and must be reported to the Sponsor within 24 hours of the site becoming aware of the event. The procedure of elective abortion should not be reported as an AE.

11.5.2 OTHER

Certain safety events, called ‘Special Situations’, that occur in association with study drug(s) may require reporting. These Special Situations include, but are not limited to, the following:

- Overdose of the medicinal product, where ‘overdose’ is defined as a subject receiving ≥ 2 times the intended dose for any given SC injection
- Suspected abuse/misuse of the medicinal product
- Inadvertent or accidental exposure to the medicinal product
- Medication error involving study drug (with or without subject exposure to the Sponsor’s medicinal product, e.g., name confusion)

Special situations should be reported whether they result in an AE/SAE or not.

12 STATISTICAL AND ANALYTICAL PLANS

12.1 ANALYSIS POPULATIONS

Further details of additional analysis populations will be described in the SAP, which will be finalized prior to study unblinding.

12.1.1 INTENTION-TO TREAT (ITT) POPULATION

The Intention-to-Treat (ITT) Population will include all randomized subjects.

12.1.2 PER PROTOCOL POPULATION

The Per Protocol Population will include all subjects in the ITT Population who have completed the 8-week Treatment Period and have no major protocol deviations.

12.1.3 SAFETY POPULATION

The Safety Population will include all subjects who have received at least 1 dose of study drug, with subjects to be analyzed based on the actual treatment received.

12.2 ANALYSIS METHODS

12.2.1 GENERAL METHODS

Details of the statistical analysis methodology will be provided in a statistical analysis plan (SAP), which will be finalized prior to study unblinding.

Continuous variables will be summarized using the number of observations, number of observations above the limit of quantification (if applicable), mean, standard deviation (SD) median, and range. Categorical variables will be summarized using frequency counts and percentages.

Once all patients have completed Week 8 of the Main Portion of the study, the study database will be locked, unblinded, and efficacy analyses for the Main Portion will be performed.

12.2.2 SUBJECT DISPOSITION

A disposition of all consented subjects will be provided and will include a breakdown of subjects who were randomized, were treated, and discontinued treatment (including reasons for discontinuation) at the Main Portion. A disposition of all consented subjects entered the Extension Portion will be also provided. Additionally, a summary of subjects included in the analysis populations defined in Section 12.1 will be provided.

12.2.3 DEMOGRAPHY AND BASELINE DISEASE CHARACTERISTICS

Demographic and baseline disease characteristics will be summarized by treatment group and overall.

12.2.4 SAFETY ANALYSIS

Safety analyses will be performed on the Safety Population.

12.2.4.1 ADVERSE EVENTS

AEs will be coded using the Medical Dictionary for Regulatory Activities (MedDRA; Version 20.0 or higher). Incidence rates for treatment-emergent AEs will be summarized overall, by maximum severity, and by relationship to study drug for each treatment group. SAEs will also be summarized by treatment group.

Incidence rates for TEAEs and SAEs will be summarized overall, by maximum severity, and by relationship to study drug. A TEAE is defined as:

- An AE that occurs after study treatment start that was not present at the time of treatment start.
- An AE that increases in severity after treatment start if the event was present at the time of treatment start.

The SAEs occurring before the first dose of study drug will be listed.

12.2.4.1.1 INFECTION

AEs related to infection with *Neisseria meningitidis* will be summarized by system organ class and preferred term.

12.2.4.2 CLINICAL LABORATORY EVALUATION

Quantitative laboratory endpoints will be summarized by treatment group at each scheduled assessment time point using descriptive statistics.

12.2.4.3 ELECTROCARDIOGRAMS

Descriptive statistics for ECG parameters [i.e., HR, PR interval, RR interval, QRS interval, QT interval, QTc interval] at each assessment time point will be presented by treatment group.

12.2.4.4 VITAL SIGNS

Descriptive statistics for vital signs (i.e., HR, body temperature, and blood pressure) will be presented by treatment group.

12.2.4.5 PHYSICAL EXAMINATION

Clinically significant physical examination abnormalities will be included and summarized as AEs, when appropriate.

12.2.5 EFFICACY ANALYSIS

Details of analyses beyond what is specified in this protocol will be discussed in detail in the SAP.

12.2.5.1 PRIMARY EFFICACY ANALYSES

The primary efficacy endpoint, percent reduction from baseline in creatine kinase at Week 8, will be compared between the two treatment groups using a 2-sided stratified Wilcoxon rank sum test (Van Elteren test). Magnitude of treatment effect will be shown by the WMWodds and the Hodges-Lehman estimator followed by the corresponding 95% Confidence Intervals (CIs).

Definition of primary estimand:

- Treatment: zilucoplan administered by daily SC injection (0.3 mg/kg) vs matching placebo.
- Target Population: is defined through the inclusion/exclusion criteria at Sections 8.1 and 8.2 of the study protocol reflecting the targeted IMNM population.
- Endpoint: percentage change from Baseline to Week 8 in CK levels while on non-prohibited medication.
- Intercurrent event: regardless of any treatment discontinuation for any reason; censoring after prohibited medication
- Population level summary: difference in ranks of the percentage change from baseline between treatments followed by the WMWodds and Hodges–Lehmann estimator followed by the corresponding 95% CIs.

12.2.5.2 SECONDARY EFFICACY ANALYSES

Secondary Estimands are defined below:

- Treatment: Zilucoplan administered by daily subcutaneous (SC) injection (0.3 mg/kg) vs matching placebo.
- Target Population: is defined through the inclusion/exclusion criteria at Sections 8.1 and 8.2 of the current document, reflecting the targeted IMNM population.
- Endpoints:
 - At least minimal response based on the ACR/EULAR minimal Response Criteria at Week 8
 - Change from Baseline to Week 8 in 3TUG Test (in ambulatory patients only);
 - from Baseline to Week 8 in Proximal MMT;
 - Change from Baseline to Week 8 in Physician Global Activity VAS;
 - Change from Baseline to Week 8 in Patient Global Activity VAS;
 - Change from Baseline to Week 8 in HAQ;
 - Change from Baseline to Week 8 in MDAAT Extramuscular Disease Activity VAS Score;
 - Change from Baseline to Week 8 in FACIT-Fatigue Scale;
 - ICE handling: regardless of any treatment discontinuation for any reason; censoring after administration of prohibited medication;
 - Population level summary:
 - Odds ratio of ACR/EULAR of ACR/EULAR ≥ 20 response proportion between treatment conditions;
 - Difference in the continuous endpoint means between treatment conditions;

The analysis to determine the odds ratio and the corresponding 95%CI for the ACR/EULAR response will be performed via logistic regression. Treatment group differences for each of the continuous secondary efficacy change from baseline endpoints will be assessed using a linear mixed effects model using the change from baseline to Week 8 as response variable; treatment, and baseline score (i.e., the baseline score for the secondary efficacy endpoint being analyzed) will be fitted as fixed effects and subject as a random effect.

Secondary efficacy endpoint analyses will be performed on the ITT Population.

12.2.6 CLINICAL PHARMACOLOGY ANALYSIS

12.2.6.1 PHARMACOKINETIC AND PHARMACODYNAMIC ANALYSES

For the PK analysis, concentrations of zilucoplan and metabolites were presented in listings and summarized using descriptive statistics.

Plasma concentration data of zilucoplan may be subjected to population PK analysis to derive population estimates of PK parameters and test the effect of various covariates such as anti-drug antibodies, age, weight, and gender. Details of the analysis will be described in a separate Data Analysis Plan (DAP). This analysis may be performed by

combining the data from the current study with data from other zilucoplan studies if deemed appropriate. The results of the population PK analysis will not be reported in the CSR but in a separate modeling report.

Pharmacodynamic endpoints will be summarized using descriptive statistics by treatment and time point.

Population PD or population PK/PD analyses may be conducted for the PD variables of interest. Details of such PD or PK/PD analyses will be described in a separate DAP. The results of the analyses will not be reported in the CSR but in a separate report.

12.2.7 INTERIM ANALYSIS

No interim analysis is planned for the Main Portion of the study.

Interim analyses of the Extension Portion of the study, after Week 8 of the Main Portion of the study has been locked and unblinded, may be performed.

12.3 SAMPLE SIZE DETERMINATION

A sample size of 12 subjects per group yields approximately 95% power to detect a difference in the percent reduction from baseline in creatine kinase between the active and placebo groups using a Wilcoxon rank sum test at the two-sided 0.05 type 1 error rate. The power calculations assume that the percent reduction in creatine kinase in the active dose group is approximately normally distributed with a mean of 80% and a standard deviation of 8%; that 4 of the placebo patients will have a percent reduction similar to the active dose group; and the remaining 8 placebo patients will have a percent reduction that is normally distributed with a mean of 10% and a standard deviation of 8% (Mammen and Tiniakou 2015).

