
• Intention-to-Treat (ITT) Population: All subjects randomized.• Per Protocol Population: All subjects in the ITT Population who have completed the 8-week Treatment Period and have no major protocol deviations.• Safety Population: All subjects who have received at least 1 dose of study drug, with subjects to be analyzed based on the actual study treatment received.		
General Considerations: A disposition of all consented subjects will be provided and will include a breakdown of subjects who were randomized, were treated, and discontinued treatment (including reasons for discontinuation).		
Continuous variables will be summarized using the number of observations, number of observations below the limit of quantification (if applicable), mean, standard deviation (SD), median, and range. Categorical variables will be summarized using frequency counts and percentages.		

Stratification of Randomization:

Subjects will be randomized in a 1:1 ratio to receive daily SC doses of 0.3 mg/kg zilucoplan or matching placebo. Randomization will be stratified based on autoantibody status (anti-HMGCR+ versus anti-SRP+).

Determination of Sample Size:

A sample size of 12 subjects per group yields approximately 95% power to detect a difference in the percent reduction from baseline in creatine kinase between the active and placebo groups using a Wilcoxon rank sum test at the two-sided 0.05 type 1 error rate. The power calculations assume that the percent reduction in creatine kinase in the active dose group is approximately normally distributed with a mean of 80% and a standard deviation of 8%; that 4 of the placebo patients will have a percent reduction similar to the active dose group; and the remaining 8 placebo patients will have a percent reduction that is normally distributed with a mean of 10% and a standard deviation of 8%. The estimation of the creatine kinase baseline levels and treatment effect are based on the data presented in Mammen et Tiniakou, 2015 (Mammen and Tiniakou 2015).

Efficacy Analyses:

The primary efficacy endpoint, percent reduction from baseline in creatine kinase at Week 8, will be compared between the two treatment groups using a 2-sided stratified Wilcoxon rank sum test (Van Elteren test).

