8.4.3 REPLACEMENT OF SUBJECTS

In order to obtain an adequate number of subjects that complete the study (see Section 12.3), additional subjects may be enrolled into the study, at the discretion of the Sponsor.

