3 SAMPLE SIZE DETERMINATION

A sample size of 12 study participants per group yields approximately 95% power to detect a difference in the percent reduction from baseline in creatine kinase between the active and placebo groups using a Wilcoxon rank sum test at the two-sided 0.05 type 1 error rate.

The power calculations assume that the percent reduction in creatine kinase in the active dose group is approximately normally distributed with a mean of 80% and a standard deviation of 8%; that 4 of the placebo patients will have a percent reduction similar to the active dose group; and the remaining 8 placebo patients will have a percent reduction that is normally distributed with a mean of 10% and a standard deviation of 8% (Mammen and Timakou 2015).

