5.1.1.2.3 Mapping of assessments performed at Early Discontinuation Visit

If a participant prematurely discontinues treatment at any time during the Main Portion, then he/she should return to the clinic for a stand-alone End of Main Visit. Corresponding assessments will be mapped to the next visit scheduled where each assessment is done as per protocol.

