5.3.2 Main analytical approach

The statistical hypothesis is stated at Section 2.1. The analysis will be conducted in the ITT using a 2-sided Van Elteren test (Van Elteren, 1960) which stands for an extension of the Wilcoxon rank sum test for comparing two treatments in a stratified experiment using within-stratum ranks assigning greater weight to rank sums from smaller strata.

The magnitude of association between groups will be expressed as in WMWodds followed by the 95% CI and by the Hodges–Lehmann estimator which quantifies the location shift.

WMWodds will be estimated based on the weighted average WMWodds for the strata. The methodology is described below:

- For each stratum the WMWOdds will be calculated via ROC analysis for the CK levels.
- The derived AUC and SE values will be used for the calculation of the stratified WMWOdds:
 $WMWodds_i = AUC_i / (1 - AUC_i)$, $i = 1, 2$

The WMWodds_i and the Standard Error (SE) will be transformed to the logarithmic scale to ensure positive values of the corresponding 95%CIs:

$$\text{LnWMWodds}_i = \text{Ln}(AUC_i / (1 - AUC_i)), i = 1, 2$$

$$\text{LnSE}_i = \text{SE}_i / (AUC_i * (1 - AUC_i)), i = 1, 2$$

- Inverse variance weights will be assigned at each strata: $W_i = 1 / (\text{LnSE}_i * \text{LnSE}_i)$, $i = 1, 2$:
- The weighted average WMWodds ($\overline{WMWodds}$) and the corresponding 95%CI can be then calculated as shown below:

$$\overline{WMWodds} = \exp \left(\frac{\sum_{i=1}^2 W_i * \text{LnWMWodds}_i}{\sum_{i=1}^2 W_i} \right)$$

$$95\%CI = \exp \left(\left(\frac{\sum_{i=1}^2 W_i * \text{LnWMWodds}_i}{\sum_{i=1}^2 W_i} \right) \pm Z_{0.025} * 1 / \sqrt{\sum_{i=1}^2 W_i} \right)$$

Additionally, for the unweighted WMWodds and Hodges–Lehmann estimator followed by the corresponding 95%CI, will also be calculated.

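### The stated 95% power holds only if exactly 4 of the 12 placebo patients respond; if 4 of 12 is read as a response probability of 1/3, power is about 85%

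*Protocol*

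**What the plan says.** Protocol 12.3 states: "A sample size of 12 subjects per group yields approximately 95% power to detect a difference" in percent CK reduction, using a Wilcoxon rank sum test at two-sided 0.05. The Synopsis ("A sample size of 12 subjects per group yields approximately 95% power") and SAP 3 ("A sample size of 12 study participants per group yields approximately 95% power to detect a difference") repeat it. The inputs are the same in all three places:

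- active arm: percent reduction normal, mean 80, SD 8;
- placebo arm: the calculation assumes "that 4 of the placebo patients will have a percent reduction similar to the active dose group";
- the other 8 placebo patients: normal, mean 10, SD 8.

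Randomization is 1:1 and stratified by antibody status only (Protocol 7.2.2.1). The primary test is the stratified Wilcoxon (Van Elteren) test (Protocol 12.2.5.1, SAP 5.3.2). Neither document gives a placebo response probability, shows power at any other responder count, or says that 4 was chosen as a cautious upper value.

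**The concern.** A power calculation fixes population parameters and lets the sample vary. Here the number of placebo responders, which is itself a sample outcome, is held at 4 while only the normal scatter around each component varies. The two placebo components are 70 points apart. The SD of a difference between two patients is 8 × √2 ≈ 11.3, so they are about 6 SDs apart and hardly overlap. The responder count is then nearly the only thing that decides whether the test rejects.

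The effect of varying the count is lopsided. Fewer than 4 responders can add at most about 5 points of power; one more removes about 17. Fixing the count at its apparent expectation therefore overstates the power of the design.

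This is the only power statement in the documents. The primary hypothesis also gates the whole secondary testing sequence (SAP 2), so a miss on CK ends formal testing.

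**Working it through.** **Inputs.** 12 per arm, two-sided 0.05, and the three normal distributions above, all from Protocol 12.3. The placebo response probability p is not in the documents; every value of p below is an assumption.

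**Step 1: rejection region.** The exact Mann-Whitney test for 12 vs 12 rejects at U ≤ 37 or U ≥ 107 (attained level 0.0449).

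**Step 2: power given k placebo responders.** With the components fully separated, each of the 12 − k non-responders lies below all 12 active patients. So U = 12 × (12 − k) + U′, where U′ is the null Mann-Whitney statistic for k vs 12.

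- k = 3: U ≥ 9 × 12 = 108, so the test always rejects.
- k = 4: 8 × 12 = 96, so U′ ≥ 11 is needed; probability 0.948. This is the plan's figure. The uncorrected normal approximation gives 96.1%.
- k = 5: 0.779.
- k = 6: 0.554.
- k = 7: 0.355.
- k = 8: 0.213.

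**Step 3: average over the count.** With independent responses, K ~ Binomial(12, p) and power = Σ P(K = k) × power(k). At p = 1/3:

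| k | P(K = k) | power(k) | product |
|---|---|---|---|
| 0–3 | 0.393 | 1.000 | 0.393 |
| 4 | 0.238 | 0.948 | 0.226 |
| 5 | 0.191 | 0.779 | 0.149 |
| 6 | 0.111 | 0.554 | 0.062 |
| 7 | 0.048 | 0.355 | 0.017 |
| 8 or more | 0.019 | 0.213 or less | 0.004 |

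The products sum to 0.850 (unrounded). P(K ≥ 5) = 0.368.

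**Step 4: range over p (exact Wilcoxon).**

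| p | power |
|---|---|
| 0.20 | 97.2% |
| 0.25 | 94.0% |
| 0.30 | 89.1% |
| 1/3 | 85.0% |
| 0.40 | 74.8% |

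Power is 95% at p = 0.236, 90% at p = 0.292 and 80% at p = 0.368.

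**Step 5: the planned test.** Van Elteren was simulated with the asymptotic test, weights 1/(N+1), response independent of stratum, and assumed per-arm stratum splits of 6/6, 7/5, 8/4, 9/3 and 10/2. Power is 93.0–94.0% with 4 responders fixed and 83.6–84.8% at p = 1/3. The like-for-like unstratified figures (uncorrected normal approximation) are 96.1% and 86.5%, so stratification costs roughly 2 to 3 points.

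**Step 6: missing Week 8 CK (illustration, p = 1/3, equal loss per arm).**

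- 22 evaluable: Van Elteren 80.5–81.3%, exact Wilcoxon 82.2%.
- 20 evaluable: Van Elteren 75.1–76.6%, exact Wilcoxon 76.9%.

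**The case against.** The strongest reply is that nothing is miscalculated. The 95% reproduces, the 4-of-12 count is printed beside it as an assumption, and 1/3 appears nowhere in the documents. Eligibility requires stable corticosteroid and immunosuppressive treatment and excludes recent rituximab and newly started IVIG (Protocol 8.1, 8.2), so 4 responders may have been meant as a pessimistic case. At p of about 24% or less the stated figure is right, and power stays at or above 80% up to about p = 0.37.

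Much of this stands. The 1/3 is an assumption, and 85% is itself conditional on it, on independent responses and on complete data. It also takes the active arm as the documents model it. If some active patients failed to respond, power would fall further: with 4 placebo responders fixed and the uncorrected normal approximation, an assumed 95% active response takes power from 96% to about 87%. If response differed by antibody stratum, Van Elteren power at an average of 1/3 could lie at about 84–87%. The Van Elteren shortfall with 4 responders fixed is small.

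What does not stand is that printing the count settles the matter. A realised count of 4 is not a population parameter, and the text presents the result as what 12 per group delivers. If 4 was a cautious choice, the documents do not say so, and a reader cannot tell a 95% design from an 85% one.

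**Conclusion.** The concern holds. The 95% is correct for its inputs but is power conditional on exactly 4 placebo responders, and it is stated as the power of the design. Taking 4 of 12 as a probability of 1/3, with independent responses, complete Week 8 CK and the active arm as modelled in Protocol 12.3, power is about 85% (Van Elteren about 84–85%). The risk of missing the assumed effect is then about three times what the plan implies: 15% against 5%. With a placebo response probability of about 24% or less, the stated figure is about right. The use of the unstratified test in the calculation is a secondary point that does not change the conclusion. The sample-size statement should be corrected; the design itself is not affected.

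**What to change.** In the Synopsis, Protocol 12.3 and SAP 3:

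1. Say whether 4 placebo responders is the expected number or a cautious upper value.
2. Either restate power as about 85% (Van Elteren about 84%) at a placebo response probability of 1/3, or keep 95%, label it as conditional on 4 placebo responders, and add the averaged figure.
3. Show the range over placebo response probability (exact Wilcoxon): 20% gives 97%, 25% gives 94%, 30% gives 89%, 40% gives 75%.
4. If missing Week 8 CK is illustrated, use Van Elteren: about 81% with 22 evaluable and about 75–77% with 20. Note there that under Protocol 8.4.3 "additional subjects may be enrolled into the study, at the discretion of the Sponsor", and that for early discontinuation SAP 5.1.1.2.3 says "Corresponding assessments will be mapped to the next visit scheduled where each assessment is done as per protocol"; both may reduce the loss.

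The cost is wording in three places and a headline figure that becomes less favourable or is labelled as conditional. Sample size, test and alpha do not change.
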